7.0 Participant Compensation

It is anticipated that subjects will be compensated for their time for participating in all phases of CHAP – completion of the health questionnaire and medical testing. It is proposed that the compensation level be \$35.00, payable upon completion of all study procedures.

8.0 Publication Policy

The study Investigator(s) has the right to publish, present or otherwise disclose his/her findings in the scientific literature with respect to data generated by the Investigator(s) from the study, subject to the following criteria:

- All final draft manuscripts, based on whole or in part on the study, must undergo a review and be approved by a Publication Steering Committee (PSC), implemented in conjunction with the community.
- Submission to the PSC for review must occur at least 60 days prior to submission by the Investigator(s) of such manuscript for publication.
- No less than 12 months must elapse following completion of the final study report before submission for publication.
- Should the PSC determine the manuscript discloses confidential or proprietary information, the Investigator(s) will either remove it or modify the manuscript to the satisfaction of the PSC, so that publication of the revised manuscript may proceed.
- Should the PSC determine the manuscript discloses any discovery, invention, or other intellectual property, which the PSC wishes to protect, whether by preparing any patent or other intellectual property applications or otherwise, the Investigator(s) will, upon request by the PSC, delay submission for a period not exceeding four months from the date the PSC receives such manuscript from the Investigator(s).
- Restrictions may be imposed on where to publish, subject to discussion with the PSC.

10.0 Appendices

The appendices outlined below appear on the following pages:

10.3.3 Instructions Specific to T.R.U.E., Given Post-Application, before Subject Departs

Appendix 10.1: Health Questionnaire

CHAP Health Questionnaire

-  indicates that the questions were derived from the HRQOL-4
 -  indicates that the questions were derived from the 2000 CCHS
 -  indicates that the questions were derived from the Smith-Sivertsen paper
- ADULT indicates adult specific
CHILD indicates child specific

The following information will be kept strictly confidential. Any information that can identify you or your family will be replaced with a unique number (as viewed at the top of this page). This identifying information will be kept separately and under restricted access.

Last Name:  _____

First Name:  _____

Middle Name: _____

Current or Former Resident: **Current / Former**

Number of People in your Household: _____

ALL MEMBERS OF HOUSEHOLD (12+) ARE TO ANSWER THE FOLLOWING QUESTIONS. SOME QUESTIONS MAY NOT APPLY (CHILD OR ADULT SPECIFIC).

Demographic Information

1. What is your date of birth? DD/MM/YYYY 

2. Please indicate your sex: 
 - Male
 - Female

3. People living in Canada come from many different cultural and racial backgrounds.
Are you: 

INTERVIEWER: Read categories to respondent. Mark all that apply.

- 1 ...White?
 - 2 ...Chinese?
 - 3 ...South Asian (e.g., East Indian, Pakistani, Sri Lankan, etc.)?
 - 4 ...Black?
 - 5 ...Filipino?
 - 6 ...Latin American?
 - 7 ...Southeast Asian (e.g., Cambodian, Indonesian, Laotian, Vietnamese, etc.)?
 - 8 ...Arab?
 - 9 ...West Asian (e.g., Afghan, Iranian, etc.)?
 - 10 ...Japanese?
 - 11 ...Korean?
 - 12 ...Aboriginal Peoples of North America (North American Indian, Métis, Inuit / Eskimo)?
 - 13 Other – Specify
-
4. How tall are you without shoes on?  (offer both ways of measuring, want metres)

 5. How much do you weigh?  (offer both ways of measuring, want kg)

6. Do you consider yourself: 
- overweight?
 - underweight?
 - just about right?
7. What is your current marital status?  ADULT
- Married
 - Living Common-law
 - Widowed
 - Separated
 - Divorced
 - Single (never married)
8. Highest grade of elementary or high school completed: 
- ___ Grade 8 or lower (Quebec: Secondary II or lower)
 - ___ Grade 9 – 10 (Quebec: Secondary III or IV; Newfoundland: 1st year of secondary)
 - ___ Grade 11 – 13 (Quebec: Secondary V; Newfoundland: 2nd to 4th year of secondary)
9. Highest degree, certificate or diploma:  ADULT
- ___ No postsecondary degree, certificate or diploma
 - ___ Trades certificate or diploma from a vocational school or apprenticeship training
 - ___ Non-university certificate or diploma from a community college, CEGEP, school of nursing, etc.
 - ___ University certificate below bachelor's level
 - ___ Bachelor's degree
 - ___ University certificate or diploma above bachelor's degree

10. Can you estimate in which of the following groups your household income falls? 

ADULT

Was the total household income ...

- Less than \$20, 000?
 - Less than \$10, 000?
 - Less than \$5, 000?
 - \$5, 000 or more?
 - \$10, 000 or more?
 - Less than \$15, 000?
 - \$15, 000 or more?
- \$20, 000 or more?
 - Less than \$40, 000?
 - Less than \$30, 000?
 - \$30, 000 or more?
 - \$40, 000 or more?
 - Less than \$50, 000?
 - \$50, 000 to less than \$60, 000?
 - \$60, 000 to less than \$80,000?
 - \$80, 000 or more?
- No Income

Residential Information

11. Please fill in the following table for your current and all past residences in Port Colborne.

Address ¹	Period of Stay ²		Type of Dwelling ³	Age of Residence ⁴
	From	To		

¹Please indicate street address, city, province, country, and postal code.

²Please indicate from MM/YYYY to MM/YYYY.

³Please indicate one of the following:

- Single Detached House
- Semi-Detached or Double (side-by-side)
- Garden House, Town-House or Row House
- Duplex (one above the other)
- Low-rise apartment (less than 5 stories)
- High-rise apartment (5 or more stories)
- Institution
- Collective dwelling (such as a Hotel/Motel, Rooming or Boarding House)
- Mobile home
- Farm or Acreage
- Other (please specify _____)

⁴Please indicate number of years.

12. If you have resided or are residing in more than one home concurrently, please fill in the following table: CHILD

Address	Percentage of Time Spent
#1	
#2	

Occupational Information

13. a) Do you now or have you ever worked in one of the following industries/occupations: Y/N ADULT.

b) If yes, please specify which industry/occupation:

- | | |
|--------------------------------|-----------------------------------|
| 1 - Underground mining | 8 - Welding |
| 2 - Smelting | 9 - Brazing |
| 3 - Metal Refining | 10 - Sintering |
| 4 - Foundry work | 11 - Plumbing |
| 5 - Steelmaking | 12 - Metal plating/electroplating |
| 6 - Metal Cutting and grinding | 13 - Shipbuilding/breaking |
| 7 - Boiler maker/repairer | 14 - Lumberyard/Sawmill |

14. If yes to question 13. a), please provide details of any employment that falls into one of the categories listed above.

	Job Description (employer, city, job title)	Job Activity	Duration of Employment (years, months)
1			
2			

Lifestyle/Dietary Information

15. What is your primary source of drinking water?

- Municipal water
- Well water
- Bottled water

16. a) Do you have a garden, or participate in a community garden? Y/N ADULT

- b) If yes, do you grow:
- flowers
 - fruits
 - vegetables

17. How frequently do you engage in each of the following non-occupational hobbies or activities? ADULT SPECIFIC

- | | |
|--------------------|---------------------------------|
| a) painting* | Never, Rarely, Sometimes, Often |
| b) landscaping | Never, Rarely, Sometimes, Often |
| c) renovations | Never, Rarely, Sometimes, Often |
| d) automotive work | Never, Rarely, Sometimes, Often |

* We are interested in paints that are known to contain metals, such as, older water-based paints (pre-1992 paint may contain mercury), older lead based paint, or hobby/artist paints (may contain metals).

18. Does anyone in this household smoke regularly inside the house? 

- Yes
- No

19. At the present time do you smoke cigarettes daily, occasionally or not at all? 

- Daily (Go to Q20)
- Occasionally (Go to Q22)
- Not at all (Go to Q24)
- DK, R (Go to Q30)

20. At what age did you begin to smoke cigarettes daily? 

__ Age (MIN: 5) (MAX: current age) (Go to Q22)

21. How many cigarettes do you smoke each day now? 

__ Number of cigarettes (MIN: 1) (MAX: 99) (Go to Q30)

22. On the days that you do smoke, about how many cigarettes do you usually have? 

__ Number of Cigarettes (MIN: 1) (MAX: 99) (Go to Q23)

23. In the past month, on how many days have you smoked 1 or more cigarettes? 

__ Number of Days (MIN: 0) (MAX: 30) (Go to Q24)

24. Have you ever smoked cigarettes daily? 

- Yes (Go to Q25)
- No (Go to Q28)
- DK, R (Go to Q28)

25. At what age did you begin to smoke (cigarettes) daily? 

__ Age (MIN: 5) (MAX: current age) (Go to Q26)

26. How many cigarettes did you usually smoke each day? 

__ Number of Cigarettes (MIN: 1) (MAX: 99) (Go to Q27)

27. When did you stop smoking daily? Was it: 
- ... Less than one year ago? (Go to Q28)
 - ... 1 to 2 years ago? (Go to Q28)
 - ... 3 to 5 years ago? (Go to Q28)
 - ... More than 5 years ago? (Go to Q28)
 - DK, R (Go to Q28)

If Q19 = (current daily or occasional smoker) or if Q19 = DK or R, go to Q30.

28. In the past month, were you exposed to second-hand smoke on most days? 
- Yes (Go to Q29)
 - No (Go to Q29)
 - DK, R (Go to Q30)

29. Does smoke from cigarettes cause you any physical irritation (for example, to your eyes, your breathing, your throat)? 
- Yes (Go to Q30)
 - No (Go to Q30)

When we use the word drink it means:

- one bottle or can of beer or a glass of draft
- one glass of wine or a wine cooler
- one drink or cocktail with 1 and a 1/2 ounces of liquor.

30. During the past 12 months, have you had a drink of beer, wine, liquor or any other alcoholic beverage?  ADULT
- Yes (Go to Q31)
 - No (Go to Q34)
 - DK, R (Go to Q36)

31. During the past 12 months, how often did you drink alcoholic beverages?  (Go to Q32)
- Less than once a month
 - Once a month
 - 2 to 3 times a month
 - Once a week
 - 2 to 3 times a week
 - 4 to 6 times a week
 - Every day

32. How often in the past 12 months have you had 5 or more drinks on one occasion? 
(Go to Q33)

- Never
- Less than once a month
- Once a month
- 2 to 3 times a month
- Once a week
- More than once a week

33. Thinking back over the past week, did you have a drink of beer, wine, liquor or any other alcoholic beverage?  (Go to Q 36)

- Yes
- No
- DK, R

34. Have you ever had a drink? 

- Yes (Go to Q 35)
- No (Go to Q36)
- DK, R (Go to Q36)

35. Did you ever regularly drink more than 12 drinks a week? 

- Yes (Go to Q 36)
- No (Go to Q36)
- DK, R (Go to Q36)

Educational Information

36. Please fill in the following table regarding all of the schools you have attended in Port Colborne up to and including high school: CHILD

School Name	Town, Province	Duration of Stay at School (YYYY to YYYY)

Other Exposure Information

37. Do you wear, or have you ever worn jewelry that pierces the skin?

- Yes
- No
- Don't Know/Refused

38. How many individual piercings do you have?

39. Did you ever have a skin irritation that was relieved by removing the jewelry?

Yes

No

Don't Know/Refused

Health-Related Quality-of-Life Measure

1. Would you say that in general your health is:  

- a. Excellent
- b. Very Good
- c. Good
- d. Fair, or
- e. Poor?

2. Recent Physical Health 

Now thinking about your physical health, which includes physical illness and injury, for how many days during the past 30 days was your physical health not good?

_____ days

3. Recent Mental Health 

Now thinking about your mental health, which includes stress, depression, and problems with emotions, for how many days during the past 30 days was your mental health not good?

_____ days

4. Recent Activity Limitation 

During the past 30 days for about how many days did poor physical or mental health keep you from doing your usual activities, such as self-care, work, or recreation?

_____ days

Current Medical Health Status

“We’d like to ask about certain chronic health conditions which you may have. We are interested in ‘long-term conditions’ that have lasted or are expected to last 6 months or more and that have been diagnosed by a health professional.” 

Respiratory:

1. Do you usually cough or clear your throat in the morning? 
 - Yes
 - No
 - Don’t Know, Refused

2. Do you cough on most days for at least 3 months of the year? 
 - Yes
 - No
 - Don’t Know, Refused

3. Do you bring up phlegm on most days for at least 3 months of the year? 
 - Yes
 - No
 - Don’t Know, Refused

4. Are you breathless when you climb two flights of stairs at an ordinary pace? 
 - Yes
 - No
 - Don’t Know, Refused

5. Are you breathless when at rest? 
 - Yes
 - No
 - Don’t Know, Refused

6. Do you have Chronic Bronchitis? 
 - Yes
 - No (Go to Q8)
 - Don’t Know, Refused (Go to Q8)

7. How old were you when this was first diagnosed? 
 - ____ Age in years
 - (MIN: 0) (MAX: current age)

8. Do you have Emphysema or Chronic Obstructive Pulmonary Disease? 
 - Yes
 - No (Go to Q10)
 - Don’t Know, Refused (Go to Q10)

9. How old were you when this was first diagnosed? 
____ Age in years
(MIN: 0) (MAX: current age)
10. Do you have food allergies? 
Yes
No (Go to Q12)
Don't Know, Refused (Go to Q12)
11. How old were you when this was first diagnosed? 
____ Age in years
(MIN: 0) (MAX: current age)
12. Do you have any other allergies? 
Yes
No (Go to Q14)
Don't Know, Refused (Go to Q14)
13. How old were you when this was first diagnosed? 
____ Age in years
(MIN: 0) (MAX: current age)
14. Do you have asthma? 
Yes
No (Go to Q17)
Don't Know, Refused (Go to Q17)
15. Have you had any asthma symptoms or asthma attacks in the past 12 months? 
Yes
No
16. In the past 12 months, have you taken any medicine for asthma such as, inhaler, nebulizers, pills, liquids, or injections? 
Yes
No

Upper Airway

17. Do you have an upper airway condition?
Yes
No (Go to Q20)
Don't Know, Refused (Go to Q20)

18. What type of upper airway condition do you have:
INTERVIEWER: Mark all that apply.

- Sinusitis
- Rhinitis
- Nasal Polyps
- Nasal Septal Ulceration
- Other, Please specify

19. How old were you when this was first diagnosed?

_____ Age in years
(MIN: 0) (MAX: current age)

Skin:

20. Do you have a skin condition?

- Yes
- No (Go to Q23)
- Don't Know, Refused (Go to Q23)

21. What type of skin condition do you have:

INTERVIEWER: Mark all that apply.

- 1 Dermatitis/eczema
- 2 Pigmentation change (skin darkening or lightening; "change in skin color")
- 3 Hyperkeratosis (skin thickening)
- 4 Other, Please specify

22. How old were you when this was first diagnosed?

_____ Age in years
(MIN: 0) (MAX: current age)

Cardiovascular:

23. Do you have high blood pressure? 

- Yes
- No (Go to Q25)
- Don't Know, Refused (Go to Q25)

24. How old were you when this was first diagnosed? 

_____ Age in years
(MIN: 0) (MAX: current age)

Remember, we're interested in conditions diagnosed by a health professional.

25. Do you have migraine headaches? 

Yes

No (Go to Q27)

Don't Know, Refused (Go to Q27)

26. How old were you when this was first diagnosed? 

____ Age in years

(MIN: 0) (MAX: current age)

27. Do you have heart disease? 

Yes

No (Go to Q29)

Don't Know, Refused (Go to Q29)

28. How old were you when this was first diagnosed? 

____ Age in years

(MIN: 0) (MAX: current age)

29. Have you ever had a heart attack (damage to the heart muscle)? 

Yes

No (Go to Q30)

30. Do you currently have angina (chest pain, chest tightness)? 

Yes

No (Go to Q31)

31. Do you currently have congestive heart failure (inadequate heart beat, fluid build-up in the lungs or legs)? 

Yes

No (Go to Q32)

Thyroid:

32. Do you have a thyroid condition? 

Yes

No (Go to Q34)

DK, R (Go to Q34)

33. How old were you when this was first diagnosed? 

____ Age in years

(MIN: 0) (MAX: current age)

Gastro-intestinal/Liver:

34. Do you have stomach or intestinal ulcers? 

Yes

No (Go to Q36)

DK, R (Go to Q36)

35. How old were you when this was first diagnosed? 

____ Age in years

(MIN: 0) (MAX: current age)

36. Do you have Gastroenteritis?

Yes

No (Go to Q38)

DK, R (Go to Q38)

37. How old were you when this was first diagnosed?

____ Age in years

(MIN: 0) (MAX: current age)

38. Do you have Jaundice?

Yes

No (Go to Q40)

DK, R (Go to Q40)

39. How old were you when this was first diagnosed?

____ Age in years

(MIN: 0) (MAX: current age)

Neurological:

40. Do you have Peripheral Neuropathy (numbness or tingling in fingers or toes)?

Yes

No (Go to Q42)

Don't Know/Refused (Go to Q42)

41. How old were you when this was first diagnosed?

____ Age in years

(MIN: 0) (MAX: current age)

42. Do you have Parkinson's Disease? 

Yes (Go to Q44)

No (Go to Q44)

Don't Know/Refused

43. How old were you when this was first diagnosed? 
____ Age in years
(MIN: 0) (MAX: current age)

Reproductive Health:

44. Were you ever diagnosed with a fertility problem?
Yes, specify
No
Don't Know/Refused

45. If female, have you ever had any of the following adverse pregnancy outcomes?
1 Spontaneous Abortion/Miscarriage
2 Still Birth
3 Ectopic Pregnancy

Other:

46. Do you suffer from multiple chemical sensitivities? 
Yes
No (Go to Q48)
Don't Know/Refused (Go to Q48)

47. How old were you when this was first diagnosed? 
____ Age in years
(MIN: 0) (MAX: current age)

48. Do you have any other long-term conditions that have been diagnosed by a health care professional? 
Yes
No (Go to Q50)
Don't Know/Refused (Go to Q50)

49. Please specify other long-term conditions. 

Drug Use:

We'd like to ask a few questions about your use of medications, both prescription and over-the-counter.

50. In the past month, did you take: 

a) ... pain relievers such as aspirin or Tylenol (including arthritis medicine and anti-inflammatories)?

Yes

No

R (Go to Mental Health Section)

b) ... tranquilizers such as Valium?

Yes

No

c) ... diet pills such Redux, Ponderal or Fastin?

Yes

No

d) ... anti-depressants such as Prozac, Paxil or Effexor?

Yes

No

e) ... codeine, Demerol or morphine?

Yes

No

f) ... allergy medicine such as Seldane or Chlor-Tripolon?

Yes

No

g) ... asthma medications such as inhalers or nebulizers?

Yes

No

h) ... cough or cold remedies?

Yes

No

i) ... penicillin or other antibiotics?

Yes

No

j) ... medicine for the heart?

Yes

No

k) ... medicine for blood pressure?

Yes

No

l) ... diuretics or water pills?

Yes

No

m) ... steroids?

Yes

No

n) ... insulin?

Yes

No

o) ... pills to control diabetes?

Yes

No

p) ... sleeping pills?

Yes

No

q) ... stomach remedies?

Yes

No

r) ... laxatives?

Yes

No

If female & age ≤ 49 ,

s) ... birth control pills?

Yes

No

If female & age ≥ 30 ,

t) ... hormones for menopause or aging symptoms?

Yes

No

DK, R

t.1) What type of hormones are you taking?

INTERVIEWER: Read categories to respondent.

- 1 Estrogen only
- 2 Progesterone only
- 3 Both
- 4 Neither

t.2) When did you start this hormone therapy?

|_|_|_| Year

(MIN: year of birth + 30) (MAX: current year)

u) ... thyroid medication such as Synthroid or Levothyroxine?

- Yes
- No

v) ... any other medication?

- Yes - Specify
- No

Mental Health Information

MOOD (Bradburn Affect Balance Scale)

The next set of questions describes some of the ways people feel at different times. Please tell me if you have the feeling often, sometimes or never.

During the past few weeks, how often have you felt:

1. ... on top of the world?
Often
Sometimes
Never
DK, R (Finished Questionnaire)
2. ... very lonely or remote from other people?
Often
Sometimes
Never
3. ... particularly excited or interested in something?
Often
Sometimes
Never
4. ... depressed or very unhappy?
Often
Sometimes
Never
5. ... pleased about having accomplished something?
Often
Sometimes
Never
6. ... bored?
Often
Sometimes
Never
7. ... proud because someone complimented you on something you had done?
Often
Sometimes
Never

During the past few weeks, how often have you felt:

8. ... so restless you couldn't sit long in a chair?

- Often
- Sometimes
- Never

9. ... that things were going your way?

- Often
- Sometimes
- Never

10. ... upset because someone criticized you?

- Often
- Sometimes
- Never

11. Taking things all together, how would you say things are these days?

Would you say you're:

- 1 ... very happy?
- 2 ... pretty happy?
- 3 ... not too happy?

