4.1.1.1.1 Inclusion Criteria

Participants may be included in the study if ALL of the following criteria apply:

- 1) They have understood and signed an informed consent form.
- 2) They are 12 years of age or older.
- 3) They live within Port Colborne boundaries.

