4.1.3 Randomization of Subjects

In general, a sample consists of the sampling units chosen from the population eligible to be included. The sampling unit is the unit around which the sampling procedure is planned, and in this study, the unit will be defined as the individual. The sampling frame is the list of all the sampling units in the population. A list of all residential telephone numbers that are publicly listed will be used in this study. This phone list is sorted by area code, and includes phone, name and address information for roughly 6,700 households. Based on the most recent aggregate data from Canada Post, this represents 85.3% (6,700/7,856) of households in Port Colborne. The sampling method is the way in which the sampling units are chosen from the sampling frame. As described above, the sampling method for this study will be a stratified random sampling approach. For stratification, the sampling frame will be divided into five geographic areas categorized by level of exposure to the CoCs. By assigning a random number to each telephone listing within each stratum and then sorting these listings by this random number, the sorted listings can be used to randomly select households for inclusion in the study. Within each household, participants will be randomly selected taking into account the number of residents. Specifically, for a household with r residents, the k th oldest resident will be chosen where k is a random number between 1 and r . The telephone interviewers will be supplied with tables of random numbers for households ranging from sizes of 2 to 10 to select a value for k .

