The estimated number of dwellings and individuals that make up the target population are listed in Table 1. This list is considered approximate as it is based on Canadian census data obtained in 1996.

Table 2: Estimated Number of Households and Individuals 12 years of Age and Older* within Each Sampling Region for the health questionnaire.

Region (EA's)	Number of private dwellings	Estimated population 12 years of age and older
1- West of the Welland Canal, south of Clarence and Augustine Road (151-156)	1,945	4,055
2- West of the Welland Canal, north of Clarence (116-120)	2,260	4,798
3- East of the Canal, south of Durham (includes Durham) and is bounded by Davis and Lake (110)	365	719
4 - East of the Canal, north of Durham (excludes Durham) and is bounded by Snider Road (106,108)	775	2,346
5- Other areas of Port Colborne (101-105,107,109,112-113)	2,030	4,437
Total	7,375	16,355

* assumes that 85% of the Port Colborne community is 12 years of age and older (based on 1996 Census data from Statistics Canada).

It is very important to note that while there are sufficient numbers to measure the prevalence of the selected health conditions with the desired precision, there is limited power to make comparisons between rates in the Rodney Street area to the remainder of Port Colborne. Specifically, with 500 subjects recruited in both the Rodney Street area and other parts of Port Colborne, the study has the power to detect an odds ratio of 2.1 for the comparison of asthma rates between the two regions with a power of 80% and a type I error rate of 5%. The odds ratio of 2.1 corresponds to a greater than two-fold increased prevalence rate in area 3 relative to the rest of Port Colborne. Similarly, for a comparison of nickel sensitivity rates in females between the two regions, there is power to detect an odds ratio of 2.2.

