6.4 Statistical Analysis

The frequency distributions of variables collected within the health questionnaire and medical tests will be tabulated. The number of missing responses for each variable will be presented, and where possible, these missing values will be treated as a separate category. Particular attention will be given to examining response rates for income levels, since this variable will be used as a proxy to socioeconomic status. If necessary, other factors, such as education, may need to be used instead.

Prevalence rates for health conditions will be calculated by age-group for males and females. Statistically significant differences across strata will be evaluated by using the Chi-Square and likelihood ratio tests for categorical data, and the Student's t-test for continuous data. Multivariate analysis of variance will be used to adjust comparisons for the influence of potential confounding variables. Comparisons will need to take into account possible differences in the age and sex structure of the populations being compared. Of particular interest will be the comparison of Area 3 (otherwise known as the Rodney Street area) to the rest of Port Colborne. Comparisons will also be made to reference data for Ontario or other normative data.

To evaluate the potential influence for response bias, where possible, socio-economic characteristics will be compared between non-respondents and participants. These variables will include: age, sex, family size, income level, and neighborhood of residence. Statistical tests of significance will be performed to determine whether non-responders differed from those who participated in the survey. Response bias will also be examined by comparing survey results obtained from the 1996 Canadian census data.

The prevalence of selected health characteristics will be compared to responses obtained from participants of the 2000 CCHS. In order to control for differences in the underlying populations, direct standardization will adjust for the age and gender make-up of the populations being compared. The ratio of these standardized rates will be calculated, and

95% confidence intervals of this ratio will be used to assess statistically significant differences.

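### The questionnaire cover has every household member aged 12+ answer, section 4.1.3 selects one resident per household, and the Area 3 sample size needs more people than that area has dwellings

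*Protocol*

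**What the plan says.** Four places in the Protocol bear on who supplies data.

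- **Section 4.1.3** defines the sampling unit: "the unit will be defined as the individual". Listed households are put in random order within stratum, and within a household of r residents "the k th oldest resident will be chosen where k is a random number between 1 and r". That gives one person per household.
- **Appendix 10.1**, questionnaire cover: "ALL MEMBERS OF HOUSEHOLD (12+) ARE TO ANSWER THE FOLLOWING QUESTIONS". The line goes on to say that some questions are specific to children or adults. The cover also has a field headed "Current or Former Resident".
- **Section 4.1.1.1.1**, third inclusion criterion: "They live within Port Colborne boundaries".
- **Section 6.1.1** expects 234 female participants in the Rodney Street area and gives a detectable odds ratio of 2.1 for asthma "with 500 subjects recruited in both the Rodney Street area and other parts of Port Colborne". Its Table 2 lists 365 private dwellings and 719 people aged 12 and older in Area 3.

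Section 6.4 plans ordinary tests: "Statistically significant differences across strata will be evaluated by using the Chi-Square and likelihood ratio tests for categorical data", with t-tests, analysis of variance and logistic regression alongside.

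**The concern.** The cover instruction and the selection rule give different answers to a basic question: how many people from a selected household enter the study? The sample size section sides with neither explicitly, but its Area 3 numbers cannot be reached with one person per dwelling.

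Each rule has its own consequence.

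- **One person per household.** The Area 3 sample is much smaller than planned, and the comparison described as of particular interest (Area 3 against the rest) loses power.
- **Several people per household.** Members share a residence, and often indoor smoke and drinking water, which the questionnaire itself records as exposures. Their metal levels and symptoms will be correlated, so a test that treats them as independent will have standard errors that are too small.
- **A mixture, left to field staff.** Selection probabilities would be unknown and the clustering uneven. Neither can be repaired after data collection.

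**Working it through.** **Inputs from the Protocol.** Section 6.1.1: asthma prevalence 5%, power 80%, type I error 5%, 500 per group, response rate 65%, half of residents female. Table 2: Area 3 has 365 dwellings and 719 people aged 12+; the city has 7,375 and 16,355. Section 4.1.3: the phone list covers 85.3% of households (6,700/7,856).

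**Assumptions.** The test is two-sided. One dwelling is one household. The city-wide 85.3% coverage applies to Area 3. The Protocol gives no within-household correlation (ICC), so 0.1 to 0.5 is used as a range.

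**1. The plan's own figures.** For two independent proportions at 5% prevalence and 500 v 500, the detectable odds ratio is 2.02 without and 2.07 with a continuity correction; the latter rounds to the stated 2.1. The female count is 719 × 0.65 × 0.50 = 233.7, i.e. 234. Both figures therefore count people and treat them as independent.

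**2. People needed per Area 3 dwelling.** 500/365 = 1.37. Even the 719 × 0.65 = 467 people implied by the female count need 467/365 = 1.28. The dwelling count is from 1996 and is described as approximate. Scaling it by the newer household total gives 365 × 7,856/7,375 = 389, still below 467 and 500.

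**3. If section 4.1.3 is followed.**
- Ceiling: 365.
- At 65% response: 365 × 0.65 = 237.
- Listed households only, at 65% response: 365 × 0.853 × 0.65 = 202.

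| Area 3 | Rest | Detectable OR, no correction | With correction | Power at OR 2.1, no correction |
|---|---|---|---|---|
| 500 | 500 | 2.02 | 2.07 | 85% |
| 365 | 500 | 2.12 | 2.18 | 79% |
| 237 | 500 | 2.30 | 2.39 | 70% |
| 202 | 500 | 2.38 | 2.48 | 66% |

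If the shortfall were made up elsewhere to keep 1,000 in total (237 v 763, or 202 v 798), the uncorrected values would be 2.19 and 2.26.

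**4. If all members aged 12+ are invited.** Mean household size is m = 719/365 = 1.97 in Area 3. The design effect is 1 + (m − 1) × ICC if everyone takes part. If each person responds independently with probability 0.65, it is about 1 + (m − 1) × 0.65 × ICC.

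| Area 3 | ICC 0.1 | ICC 0.5 |
|---|---|---|
| Design effect, 65% respond | 1.06 | 1.32 |
| Effective number per 500 | 470 | 380 |
| True level of a nominal 5% test | 5.7% | 8.7% |
| Design effect, all respond | 1.10 | 1.48 |
| Effective number per 500 | 456 | 337 |
| True level of a nominal 5% test | 6.1% | 10.8% |

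City-wide, m = 16,355/7,375 = 2.22, and the design effect is 1.08 to 1.40 at 65% response.

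**The case against.** The best defence is that the cover line does not control enrolment. Under section 4.2.4 a person is first randomly selected, then contacted and scheduled. At the visit the name is checked against the appointment book, photo identification is checked and individual consent is signed. Only then does a nurse administer the form, which has space for one name and one date of birth. The line can be read as a clumsy note on which questions apply to which ages. This stands in part: the documents do not show that unselected relatives would be enrolled. It does not dispose of the point, because nothing in the Protocol says which text prevails, and the Area 3 figures in section 6.1.1 also need more than one person per dwelling.

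A second objection is that allowance for clustering is commonly left to a statistical analysis plan. That is fair, and the missing household term is not criticised here. How many people are enrolled per household is different: the Protocol fixes it, and fixes it in incompatible ways.

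Three stronger readings are tempting but not supported.

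- **That the unit of analysis differs.** Both texts use the individual; what differs is the number taken per household and the resulting clustering.
- **That former residents are admitted.** The Current / Former entry is a data field. Eligibility is set by the residence criterion in 4.1.1.1.1, and selection starts from listed Port Colborne households.
- **That the tests in section 6.4 are invalid as planned.** If 4.1.3 is followed there is no household clustering, and that loss is zero.

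**Conclusion.** The inconsistency is real and affects who is enrolled, so it is more than a clerical slip. The cover of Appendix 10.1, section 4.1.3 and section 6.1.1 cannot all be met.

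Under one person per household, the detectable asthma odds ratio moves from the stated 2.1 to about 2.3 to 2.4 (2.4 to 2.5 with the continuity correction that reproduces 2.1). Power at 2.1 is about 66% to 70%. This rests on 65% response, one household per dwelling and 500 subjects elsewhere.

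Under several per household, the penalty is modest to moderate: a design effect of about 1.06 to 1.32 in Area 3 at 65% response, with 1.48 as the upper end under full participation. Its size depends on an assumed correlation, and it arises only if co-residents are in fact enrolled.

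The residency field is a minor inconsistency with no shown effect on any estimate.

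**What to change.** Decide before fielding how many people per household are to be enrolled, and make the three places agree.

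- **If section 4.1.3 stands:** change the cover line to say that only the household member selected under 4.1.3 answers, and that some questions apply to adults or children only. Restate the Area 3 target, the expected number of women and the detectable odds ratios in section 6.1.1 from 365 dwellings, the response rate and the list coverage. Weights should reflect the 1/r chance of selection within a household.
- **If several members are meant:** rewrite 4.1.3 to say who is invited, record a household identifier, and use household-clustered variance (survey methods or generalised estimating equations). State the assumed correlation in the sample size section.

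In either case, remove the Current / Former field or explain its purpose.

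The form edit is two lines. The first option also needs section 6.1.1 recalculated and a smaller Area 3 sample accepted. The second needs a new selection paragraph and a clustered analysis. Editing the cover alone would leave the Area 3 numbers out of reach.
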